6.1 Data collection

6.1.1 Demographics and knowledge

Demographic data including age, gender, post-graduate-year level, specialty, previous advanced cardiac arrest experience and training as well as simulation experience will be collected in the initial and retention phase after a short standardized accommodation phase.

6.1.2 Performance Assessment

Non-Technical Skill

Non-technical skills for crisis resource management including leadership, communication skills, problem solving, resource utilization, situation awareness and overall performance will be evaluated by using the established and validated Ottawa Global Rating Scale.^{23,24} Two blinded, independent expert raters will review all video recorded scenarios. Both raters will be intensively trained in using the checklist prior to the start of the study in order to improve inter-rater reliability. The same two raters will assess all scenarios.

Technical Skill

Technical skill performance will be measured by using a task specific checklist. For this purpose we will use an internally validated and adapted version of the American Heart Association's Megacode Checklist. The main items will be the team leader performance, management of the initial tachycardia, management of the pulseless electrical activity and the actions taken during the following ventricular fibrillation. Post resuscitation care will not be assessed to guarantee the blinding of the investigators. Therefore a total score of 18 points instead of 21 will be reachable. Furthermore the overall performance will be rated using "pass" and "fail". The same two investigators who assessed for non-technical skills will assess all scenarios for technical skills as well.

6.1.3 Stress Assessment

Acute stress will be assessed by means of salivary cortisol, the State-Trait Anxiety Inventory (STAI) and questionnaire aligned with the cognitive appraisal theory.^{4,5,10,25}

Salivary Cortisol

The activation of the hypothalamic-pituitary-adrenal axis as surrogate for psychological stress will be measured using salivary cortisol levels that show a close to linear relationship to plasma cortisol levels.^{4,5,26} Cortisol levels will be measured in both simulation tests (initial test and retention test). Salivary cortisol peaks at 20 to 40 minutes after the onset of a stressor.⁴ In order to approach cortisol kinetic, 5 cortisol samples will be obtained per participant per scenario: when participants arrive at the simulation center (sample 0), just before each scenario (sample 1), immediately at the end of the each scenario (sample 2), 30 minutes after the start of the scenario (sample 3), and at the end of the debriefing phase (sample 4). The cortisol sampling schedule for the initial and the retention test will be identically, resulting in a total of 10 cortisol samples per participants (see Appendix D). A roll shaped synthetic saliva collector (Salivette for Cortisol testing, Starstedt, Montreal, Quebec, Canada) will be used and will be frozen at -20°C until analysis using an ELISA technique at the Technische Universität Dresden, Germany.

State-Trait Anxiety Inventory (STAI)

To evaluate acute and subjective stress the standardized test battery of the STAI will be used. With STAI state anxiety at the very given moment can be measured using 20 statements to which the participants agree or disagree on a four point Likert-like scale (1 – not at all, 4 very much so). The sub scores are summed up and provide a sensitive basis for acute changes in anxiety related to stressful simulation.^{10,25} STAI will be assessed after the resting phase before each scenario and immediately after the debriefing of the initial and the retention scenario.

Cognitive Appraisal

Cognitive appraisal will be measured at the end of each scenario briefing and immediately after the scenario using the method described by Tamoka et al. and evaluated for the use in simulation by Harvey et al.^{10,27,28} Primary appraisal (demand) will be measured by asking the question “How demanding do you expect the upcoming task to be?” before the scenario and “How demanding was the task you just completed?” after the scenario. Secondary appraisal (resources) will be assessed at both times by asking “How able are/were you to cope with this task?” 10 point Likert-like scale will be used for this assessment. A cognitive appraisal index will be calculated thereafter by dividing results of primary appraisal by results of secondary appraisal. An index <1 will indicate that resources do not meet demands and the task is appraised as “threat” while an index >1, where resources are greater than demands will indicate a “challenge”.

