6. METHODOLOGY

Institutional ethics approval will be sought from the Ottawa Hospital Research Ethics Board and the University of Toronto Research Ethics Board for Health Sciences. Informed consent and a confidentiality agreement will be obtained from participants. Participants will be enrolled after approval from their resident site coordinator. They are asked to refrain from physical strains, smoking, drinking caffeinated or low pH beverages and eating for at least one hour before participating. The trial will be conducted between 11 AM and 8 PM to warranty stable cortisol levels. All participants will be asked to switch off their mobile phones and pagers in order to prevent distraction during the study.

Initial Test

After a standardized accommodation phase of 15 minutes, all participants will be exposed to a prerecorded, 15 minute long video-review of the actual advanced cardiac life support algorithms. We will collect baseline data including demographic data, stress markers and data on anxiety thereafter as described below.

Immediately before a short scenario briefing the participants will be randomized to either the intervention (unexpected death) or control (survive) group. Participants from both groups will have to individually manage a simulated in-hospital cardiac arrest scenario as team leader (Appendix C). At the initial test, in the intervention group (unexpected death), the scenario will be designed to ultimately lead to the death of the simulation mannequin, regardless of the participant's performance. In the control group (survive), the mannequin will survive. We will attempt to ensure that participants do not anticipate the series of events in the retention resuscitation scenario based on their experience during the initial resuscitation scenario (recall bias). Therefore, the scenarios will be different in terms of order of the presenting arrhythmia. For example the participant who manages a patient with ventricular fibrillation (VF), then pulseless electrical activity (PEA), followed by asystole in the initial scenario will go on to manage a patient with pulseless electrical activity (PEA), then ventricular fibrillation (VF), then return of spontaneous circulation (ROSC) in the retention test. The clinical stems of the scenarios in the initial test versus the retention test will also

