6.2 Randomization

In order to create groups of participants that are similar in regards of their baseline characteristics and in order to increase the power of our study we will use the approach of stratified randomization to allocate the participants to the intervention and control group. In order to keep the number of strata and the resulting covariates small we will stratify the participants regarding their level of training (PGY1 – PGY3 residents, vs. PGY4 – PGY 5 residents and fellows), their likelihood of providing acute care (acute care specialties will include anesthesia, emergency medicine and critical care trained personnel). Thereafter computer block randomization will be performed using the algorithm provided at www.randomization.com for all subgroups. Participants will be assigned to the

intervention (initial test ending with asystole) and control (initial test ending with sinus rhythm) groups in a 1:1 ratio. To ensure even allocation to the intervention and control group blocks of 4 participants will be predefined. Sealed, numbered, opaque envelopes, containing the random allocation, will be opened after the resting period immediately before scenario briefing begins.

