Impact of Unexpected Death in Simulation: Skill Retention, Stress and Emotions

Data Analysis Plan

Primary Outcome: Difference in retention of non-technical crisis resource management (CRM) skills using Ottawa Global Rating Scale (OGRS)

ANCOVA:

- Dependent variable: OGRS score (total score)
- Independent variable: Death vs. survival
- Covariates: Junior vs. senior; Acute vs. non-acute

Secondary Outcome 1: Technical CRM skills (according to checklist)

- Same Videos to be provided for primary outcome will be scored using the “Task-specific checklist” (derived from American Heart Association’s Megacode Checklist) and given a score out of 18

ANCOVA:

- Dependent variable: Task-specific checklist score (total score)
- Independent variable: Death vs. survival
- Covariates: Junior vs. senior; Acute vs. non-acute

Secondary Outcome 2: Stress

Measure 1: Salivary cortisol

Five time points (minutes passed since baseline):

1. Baseline (0 minutes) during the accommodation period at the beginning of the day
2. Before scenario (10 minutes)
3. Immediately after scenario (30 minutes)
4. 30 minutes after start of scenario (45 minutes)
5. After debrief (50 minutes)

ANCOVA:

- Dependent variable: Change in cortisol concentration (versus baseline) at a given time point (for each time point)
- Independent variable: Death vs. survival
- Covariates: Junior vs. senior; Acute vs. non-acute

Regression:

- Linear regression to determine the effects of covariates (Junior vs. senior; Acute vs. non-acute) on change in cortisol concentration over time
 - Separated into “death” and “survival” groups
 - Change in cortisol concentration will be established using the baseline reading of each participant on each day of the study (time point 1).
- Unpaired t-tests will be used to compare change in cortisol levels between the “death” group and the “survival” group at each time point.

Measure 2: State-Trait Anxiety Inventory (STAI)

- Analysis will be carried out in the same way as the cortisol measures with the STAI score taking the place of the change in cortisol concentration

Measure 3: Cognitive appraisal

- Mean cognitive appraisal ratios for each group (“death” and “survival”) at each time point will be calculated and subjected to a one-sample t-test to determine whether they are significantly different from 1.
- Unpaired t-tests will be used to compare the mean ratios of the “death” and “survival” groups at each time point.

Secondary Outcome 3: Valence of emotions

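### The STAI analysis leaves the pre-randomisation STAI unused as a covariate and should say outright that the outcome is the score, not a change (minor)

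*Protocol*

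**What the plan says.** Protocol 6.1.3 gives two STAI readings per test day: "STAI will be assessed after the resting phase before each scenario and immediately after the debriefing of the initial and the retention scenario". It describes the instrument as a measure of the present state: "With STAI state anxiety at the very given moment can be measured".

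Two sections place the first reading before allocation. Protocol 6 (Initial Test), after describing the accommodation phase and the video review, says "We will collect baseline data including demographic data, stress markers and data on anxiety thereafter as described below", and then "Immediately before a short scenario briefing the participants will be randomized". Protocol 6.2 says the envelopes "will be opened after the resting period immediately before scenario briefing begins".

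The SAP handles STAI in one sentence under Secondary Outcome 2, Measure 2. It refers back to the cortisol analysis, "with the STAI score taking the place of the change in cortisol concentration". That cortisol analysis has three parts:

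- an ANCOVA by group, adjusted for junior/senior and acute/non-acute, whose dependent variable is "Change in cortisol concentration (versus baseline) at a given time point (for each time point");
- a linear regression on the two strata, run separately in each group, with change worked out "using the baseline reading of each participant on each day of the study";
- unpaired t-tests between groups at each time point.

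Protocol 7.3 names the same two strata as the ANCOVA covariates. Neither document uses an earlier STAI value as a covariate.

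**The concern.** Two things follow from defining the STAI analysis only by reference to cortisol.

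First, a baseline value of the same questionnaire is available for every participant before allocation and is not used. Adjusting for it is a standard way to sharpen a randomised comparison in a trial of this size. The inherited t-tests adjust for nothing, so STAI also gets an adjusted and an unadjusted test of the same contrast, with no statement of which one counts.

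Second, the cortisol template is built on change from a same-day baseline. If an analyst carries that rule over, the pre-retention STAI becomes the retention-day baseline. That reading comes three months after the intervention. Secondary objective (ii) in Protocol 4.2 asks about later stress, and anticipatory anxiety before the second scenario may be part of that effect. Under a change score it would have no group comparison of its own and would be subtracted from the later reading.

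**Working it through.** **Plan's own figure.** The documents give no sample size, SD, correlation or effect for STAI. The primary-outcome calculation in Protocol 7.2 reproduces: a two-sample t-test with d = 0.8, two-sided 0.05 and power 0.80 needs 52; 52 × (1 − 0.12) = 45.76, so 46; and 46 × 1.2 = 55.2, so 56. I use 56 for the initial test and 46 for three months.

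**Is the first STAI a true baseline?** Protocol 6 puts the baseline anxiety data ahead of randomisation, and Protocol 6.2 opens the envelope only after the rest period. Participants are also blinded to their assignment at that stage (Protocol 6.3). The value cannot carry a treatment effect, so it is a legitimate covariate.

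**What a change score does on retention day.** Let D_pre and D_post be the group differences in STAI before the retention scenario and after its debriefing. The change-score contrast is D_post − D_pre. If the earlier death raises anticipatory anxiety, D_pre is above zero and is removed from the estimate. At the pre-retention reading itself the change is zero for everyone, so nothing is compared.

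**Precision.** Assumptions: equal SDs at both readings, 1:1 allocation, and r the partial correlation between the initial pre-scenario STAI and the later STAI given the strata. All values of r are assumed. The detectable difference, in SDs of one STAI score, is

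λ × √(4/N) × k,

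where λ is the noncentrality giving 80% power in a two-sided 5% t-test, and k is:

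- raw score: k = 1, df = N − 4;
- change score: k = √(2(1 − r)), df = N − 4;
- score adjusted for initial STAI: k = √(1 − r²), df = N − 5.

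Initial test, N = 56, √(4/56) = 0.267; λ = 2.855 (df 52) or 2.856 (df 51):

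| r | raw | change | adjusted |
|---|---|---|---|
| 0.3 | 0.763 | 0.903 | 0.728 |
| 0.5 | 0.763 | 0.763 | 0.661 |
| 0.7 | 0.763 | 0.591 | 0.545 |

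Three months, N = 46, √(4/46) = 0.295; λ = 2.868 (df 42) or 2.869 (df 41). Lower correlations are assumed because of the interval:

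| r | raw | adjusted |
|---|---|---|
| 0.1 | 0.846 | 0.842 |
| 0.2 | 0.846 | 0.829 |
| 0.3 | 0.846 | 0.807 |

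**Price of the extra covariate.** If r were zero, the lost degree of freedom would move the detectable difference from 0.7629 to 0.7632 SD at N = 56. The change score is worse than the raw score when r is below 0.5 and better above it. The adjusted analysis is at least as precise as both at every r in the tables.

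**The case against.** The best defence is that the SAP sentence is clear enough: the STAI score takes the place of the change, so the outcome is the raw score. That is the most natural reading. A reader might infer that the STAI analysis is undefined or that the two readings are equally likely, and the documents do not support that. What remains is a residual doubt from the imported baseline rules, which one sentence would remove. The four measurement times are also not missing, since Protocol 6.1.3 fixes them.

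A second defence is that adjusting only for the strata is a deliberate choice (Protocol 7.3), that the unadjusted analysis is valid, and that Protocol 8.2 regards all results as hypothesis generating. This stands as an argument about weight. At r = 0.3 the gain at the initial test is only about 5% (0.763 to 0.728 SD). It does not stand as a reason to leave out a baseline that is already collected.

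A reader might also infer that measuring STAI only after the debriefing is an error that hides the acute response. It is a limitation of interpretation. The contrast is a valid randomised comparison of anxiety after the whole session, and the cortisol samples at and soon after scenario end, together with the immediate post-scenario appraisal, cover the acute window. No size can be derived. The two remarks in Protocol 6.4.2 on stress returning to normal concern different sets of sessions and are compatible, and neither reports STAI after simulated death.

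**Conclusion.** The point holds as a minor one. The initial pre-scenario STAI is a pre-allocation value that the plan leaves unused. The loss is in precision alone, and it would be wrong to infer bias. With 56 analysed, the detectable difference would fall from 0.76 SD to 0.73, 0.66 or 0.55 SD at r = 0.3, 0.5 or 0.7. With 46 at three months it would fall from 0.846 SD to 0.842, 0.829 or 0.807 SD at r = 0.1, 0.2 or 0.3, which may be negligible. These figures rest on assumed correlations and equal SDs, for which the documents give no values.

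The change-score reading is the less natural one, but it would alter the question asked on retention day, so it should be closed off before analysis. The effect is confined to one of three stress measures within a secondary outcome. The primary analysis and the sample size are untouched.

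**What to change.** Reword SAP Measure 2 as follows:

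1. State that the dependent variable is the STAI score at each reading and that no change score is used.
2. For the initial post-debriefing, pre-retention and retention post-debriefing STAI, use ANCOVA on group with the initial pre-scenario STAI, junior/senior and acute/non-acute as covariates.
3. Say explicitly that this ANCOVA replaces the unadjusted t-tests as the group comparison for STAI. The within-group regression on the strata is not a group comparison. If it is kept, it should use the score as well.
4. Do not use the pre-retention STAI as a baseline or covariate, because it is taken after the intervention.
5. Interpret the retention post-debriefing contrast as earlier death combined with the current outcome, since the mannequin's outcome is switched between groups on that day (Protocol 6, Retention Test and Both Phases).
6. Note, when STAI is read as acute stress, that the only post-scenario reading follows the debriefing.

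Protocol 7.3 should mention the added covariate so that the two documents agree. No new data are needed. The statistical cost is one degree of freedom.

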3. BACKGROUND

Trainers are more frequently employing high-fidelity medical simulation to allow learners to acquire complex skills at minimal risk to real patients.¹ The presence of critical observers during such training invokes a stress response and emotional reactions in participants. Invoking emotional responses, both positive and negative, appears to enhance the participant's memory of the event and can ameliorate learning.² Some educational researchers take advantage of such responses to overcome the challenges presented by workload, rising expectations, and resource limitations to create a memorable simulation learning event.

The utility of stress for enhancing learning is controversial and its use may be a net negative.^{2,3} Stress is closely associated with anxiety and is generally considered a negative occurrence. Cognitive appraisal theory considers the perception of whether the resources available to a person facing a stressful incident are adequate; if they are, then the situation is viewed as a challenge whereas inadequate resources cause the situation to be seen as a threat. Situations perceived as a threat invoke anxiety in the subject and activate biological pathways, specifically in the sympathetic nervous system and the hypothalamic-pituitary-adrenal axis.^{4,5} Endocrine activity causes the subject to be more attentive and perceptive and to develop stronger memories of the threatening events.⁶⁻⁹ There appears to be a direct correlation between the cortisol levels in an individual during an event and the degree of retention of the memory of that event, though heightened cortisol may negatively affect the recall of older memories during the event.⁶ Despite the promising evidence in favour of heightening cortisol during learning, educators almost must consider the consequences of inflicting negative emotions and stress onto participants. The positive effects of cortisol on memory decay as cortisol concentrations increase, ultimately causing impairment of learning and performance at very high levels.⁸ On the other hand, situations appraised as a challenge are not accompanied by cortisol release and may result in less retention.¹⁰

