7.3 Statistical analysis

As it has been suggested as best practice for stratified randomized controlled trials, ANCOVA will be used to analyze the outcome parameters using the level of training (PGY1-3 vs PGY 4-5 and fellows) and specialities (acute care specialities vs. non-acute care specialities) as covariates.³⁵ Group assignment (unexpected death, alive) will be used as the independent variable. Demographic data will be analyzed using an unpaired Student's *t*-test or chi-square test, where appropriate.

Curved/linear regression analysis will be performed to assess the correlations between each outcome and stress as well as emotions. As it is common practice, results of Likert-like scales will be treated as interval-measures and thereby analyzed by using parametric tests.^{36,37}

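### The cognitive appraisal index is demand divided by resources, but its threat and challenge cut-offs are those of the inverse ratio, and the SAP gives no direction

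*Protocol*

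**What the plan says.** Protocol 6.1.3 (Cognitive Appraisal) calls the rating of how demanding the task is the primary appraisal, and the rating of ability to cope the secondary appraisal (resources). Both use a 10-point scale, before and after each scenario. The index comes from "dividing results of primary appraisal by results of secondary appraisal". Two interpretations follow. The first is "An index <1 will indicate that resources do not meet demands and the task is appraised as" a threat. The second is a value above 1, "where resources are greater than demands will indicate a" challenge.

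Protocol section 3 gives the theory. If resources are adequate, "then the situation is viewed as a challenge whereas inadequate resources cause the situation to be seen as a threat".

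The SAP (Secondary Outcome 2, Measure 3) says "Mean cognitive appraisal ratios for each group" at each time point will be calculated and "subjected to a one-sample t-test to determine whether they are significantly different from 1". For the group contrast it says "Unpaired t-tests will be used to compare the mean ratios of the" two groups. It names no numerator, denominator, direction or label. Protocol 7.3, by contrast, says "ANCOVA will be used to analyze the outcome parameters using the level of training" and specialty as covariates.

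**The concern.** The formula and its interpretation point in opposite directions. The verbal meanings agree with section 3, so the slip is either in the order of division or in the inequality signs. The documents do not show which, and the SAP does not settle it.

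Cognitive appraisal is a named component of the secondary stress outcome (protocol 7.1.2) and bears on secondary objectives (ii) and (iii). If the text is applied literally, a group under threat is reported as challenged, against the protocol's own theory. The sign of every association involving the ratio, in the regressions of protocol 7.3 and in the SAP's matrix of relationships, is unclear in the same way.

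Two lesser points follow. The SAP treats a mean ratio of 1 as balance, which a ratio of two varying ratings does not generally satisfy. And its unpaired t-test departs from the ANCOVA stated in the protocol.

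**Working it through.** **Inputs.** From the documents: demand D is the primary appraisal, resources R the secondary, index = D/R, with cut-offs below 1 = threat and above 1 = challenge. Assumed: scores run from 1 to 10 and higher means more demanding or more able, because the anchors are not stated.

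**Labels.** D/R < 1 holds exactly when D < R, which is when resources exceed demand. The stated rule calls that a threat.

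- D = 8, R = 4: index 8/4 = 2.0. The rule says challenge; the protocol's wording (resources short) says threat.
- D = 4, R = 8: index 4/8 = 0.5. The rule says threat; the wording says challenge.

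Of the 10 × 10 = 100 possible pairs, 10 are ties (index 1, given no label) and 90 are untied.

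| Definition | Untied pairs contradicting the wording |
|---|---|
| D/R with the stated cut-offs | 90 of 90 |
| D/R with the cut-offs reversed | 0 of 90 |
| R/D with the stated cut-offs | 0 of 90 |
| D/R with the stated cut-offs, both items reverse-scored (11 − score) | 0 of 90 |

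**Does the choice of ratio affect the test?** Take the two participants above as a group. Mean D/R = (2.0 + 0.5)/2 = 1.25. Mean R/D = (0.5 + 2.0)/2 = 1.25. Mean D − R = (4 − 4)/2 = 0. The ratings are balanced, yet both mean ratios exceed 1. In general, if D and R have the same distribution, log(D/R) has mean 0. The exponential is convex, so the expected ratio exceeds 1 in both directions unless D and R are always equal.

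To size this, ratings were simulated as bivariate normal values rounded and clipped to 1-10, with 20,000 replicates per equal-SD cell, 40,000 per unequal-SD cell, and two-sided 5% one-sample t-tests. The group size is 28 (56/2 recruited) or 23 (46/2, the number protocol 7.2 says is needed before allowing for attrition). The documents give no rating distributions, so all means, SDs and correlations are assumed.

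| Assumed ratings | Expected D/R | Upward rejections (nominal 2.5%) |
|---|---|---|
| Equal means 5.5-7, equal SDs 1.5-2, correlation −0.3 to 0.3 | 1.04-1.30 | 7-15% at n = 28; 5-11% at n = 23 |
| Same means and correlations, SD 1 | 1.02-1.05 | 5-8% at n = 28 |
| Means 6, SDs 2 (D) and 1 (R), correlation 0.8 | 0.983 | 1.3% at n = 28 (4.5% downward) |

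In the last row the inverse ratio has expectation 1.112 and rejects upward in 15.6% of data sets, so the two ratios lead to different conclusions. There the log ratio rejects in 10.8% in total, and demand minus resources in 5.0%. Across the equal-SD cells at n = 28 the difference rejects in 4.7-5.2%. In five of those cells, the sample means of D/R and R/D were both above 1 in 51-87% of data sets.

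**Group comparison.** Assumed: 56 completers, four equal strata, 1:1 within each, strata explaining 11% of variance (near the r² of 0.12 in protocol 7.2), and an effect of 0.8 within-stratum SD. Over 40,000 replicates the unpaired t-test has actual size 3.9% and power 80%; ANCOVA has 5.2% and 83%. The t-test is conservative, not biased.

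**The case against.** - **Reverse scoring.** The stated rule is consistent if high scores mean less demanding and less able. The anchors are not given, so this is not strictly excluded. But the items ask how demanding the task is and how able the participant is, and nothing in either document suggests reverse scoring. If it was intended, it too must be written down.
- **The 90 of 90 count only restates a reversed inequality.** That is fair: it shows the error is complete, not that it is large. No SAP test uses the labels, so the harm lies in interpretation.
- **The SAP can inherit the protocol's division.** It can, and then only the signs need correcting. But the protocol contradicts itself, so the reader cannot know that the division is the part to keep.
- **The mean-ratio point is a choice of estimand.** This stands. Where the true mean ratio exceeds 1, rejecting a mean of 1 is not an error under the SAP's literal null. It misleads only if 1 is read as balance between demand and resources, which the cut-offs invite. On a two-sided basis the total rejection rates at n = 28 are about 7-15% against 5%, and the unequal-SD example shows the shift can reverse.
- **The log ratio does not rescue the test in that example.** This also stands: it rejects more often there than D/R does (10.8% against 1.3% + 4.5% = 5.8%).
- **The t-test departure costs little.** Agreed. It is minor and adds no weight to the main point.

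**Conclusion.** The contradiction holds under the natural scoring of the two items. Formula and cut-offs cannot both be applied, and the SAP leaves the direction open. Applied literally, threat and challenge are swapped for every participant whose two ratings differ.

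The reach is limited: one of three measures within the stress outcome, with no effect on the primary outcome, the sample size or any p-value for a ratio already chosen. It should still be settled before the data are seen, because choosing between D/R and R/D can change the one-sample result.

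The shift of the mean ratio away from 1 is secondary and depends on the assumed distributions. The unpaired t-test is a minor inconsistency between the documents.

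**What to change.** Before analysis, put the same definition in protocol 6.1.3 and in the SAP under Measure 3. Either version is coherent:

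- demand/resources, with values above 1 read as threat and below 1 as challenge; or
- resources/demand, with values below 1 read as threat and above 1 as challenge.

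State the scale anchors and how an index of exactly 1 is classified.

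Test balance as mean demand minus resources against 0. Use the log ratio against 0 only if relative balance is the stated target, since the log ratio answers a different question from equal mean ratings.

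Replace the unpaired t-test with the ANCOVA on the two stratification factors that protocol 7.3 already specifies. Neither document adjusts for baseline appraisal. If that is added, use only the initial-test pre-scenario value, because the retention-day value follows the exposure.

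The cost is one corrected sentence in the protocol and a short definition with test wording in the SAP. No new data and no change in sample size are needed.
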